8.4. Guidelines for Evaluation of Measurable Disease

All measurements should be taken and recorded in metric notation using a ruler or physical calipers. All baseline evaluation studies should be performed as closely as possible to the beginning of treatment and never more than 4 weeks before the beginning of treatment. The same method of assessment and the same technique should be used to characterize each identified and reported lesion at baseline and during follow-up. Imaging-based evaluation is preferred to evaluation by clinical examination when both methods have been used to assess the antitumor effect of a treatment.

Clinical lesions. Clinical lesions will only be considered measurable when they are superficial (e.g., skin nodules and palpable lymph nodes). In the case of skin lesions, documentation by color photography, including a ruler to estimate the size of the lesion, is recommended.

Chest x-ray. Lesions on chest X-ray are acceptable as measurable lesions when they are clearly defined and surrounded by aerated lung. However, cross sectional imaging is preferable.

Multidetector CT, PET/CT and MRI. These techniques should be performed with contiguous slices of 5 mm or less in thickness. This applies to tumors of the neck, chest, abdomen and pelvis. Head and neck tumors and those of extremities may require specific imaging protocols or evaluation with ultrasound. When the primary endpoint of the study is objective response evaluation, US should not be used to measure tumor lesions. It is, however, a possible alternative to clinical measurements of superficial palpable lymph nodes, subcutaneous lesions, and thyroid nodules. US might also be useful to confirm the complete disappearance of superficial lesions usually assessed by clinical examination.

Endoscopy, Laparoscopy. These will not be used to assess response on this study.

Tumor markers. Tumor markers alone cannot be used to assess response. If markers are initially above the upper normal limit, they must normalize for a patient to be considered in complete clinical response.

Cytology, Histology. These techniques can be used to differentiate between partial responses (PR) and complete responses (CR) if clinically indicated.

8.5. Response Criteria

8.5.1. Immune Related Response Criteria (irRC)

Evaluation of Target Lesions

Response in new patients will be conducted using the Immune Related Response Criteria (irRC), as described by (12). "For irRC, only index and measurable new lesions are taken into account. At the baseline tumor assessment, the sum of the products of the two largest perpendicular diameters (SPD) of all index lesions (five lesions per organ, up to 10 visceral lesions and five cutaneous index lesions) is calculated. At each subsequent tumor assessment, the SPD of the index lesions and of new, measurable lesions ($\geq 5 \times 5\text{mm}$; up to 5 new lesions per organ: 5 new cutaneous lesions and 10 visceral lesions) are added together to provide the total tumor burden."

For the purposes of this study, 3 separate tumor burdens will be calculated for each patient and used to define 3 separate irRCs as discussed in 8.3. All criteria will be considered separately for all 3 irRCs: global, in-field, and out-field.

Global Tumor Burden = SPD(all index lesions) + SPD(new, measurable lesions)

In-Field Tumor Burden = SPD(all index lesions targeted by SBRT in this protocol) + SPD(new, measurable lesions inside the SBRT PTV)

Out-Field Tumor Burden = SPD(all index lesions NOT targeted by SBRT in this protocol) + SPD(new, measurable lesions outside the SBRT PTV)

Complete Response (irCR): irCR, complete disappearance of all lesions (whether measurable or not, and no new lesions) confirmation by a repeat, consecutive assessment no less than 4 wk from the date first documented.

Partial Response (irPR): irPR, decrease in tumor burden $\geq 50\%$ relative to baseline confirmed by a consecutive assessment at least 4 wk after first documentation.

Progressive Disease (irPD): irPD, increase in tumor burden $\geq 25\%$ relative to nadir (minimum recorded tumor burden) confirmation by a repeat, consecutive assessment no less than 4 wk from the date first documented.

3. If a patient is classified as having irPD at a post-baseline tumor assessment, then confirmation of irPD by a second scan in the absence of rapid clinical deterioration is required. The definition of confirmation of progression represents an increase in tumor burden $\geq 25\%$ compared with the nadir at two consecutive time points at least 4 wk apart. It is recommended that this be done at the discretion of the investigator because follow-up with observation alone may not be appropriate for patients with a rapid decline in performance status.

Stable Disease (irSD): irSD, not meeting criteria for irCR or irPR, in absence of irPD. In contrast to other response criteria, this criteria does not require repeat confirmation. Clinical benefit will be established as having irSD for up to 6 months for irSD.

The following two tables are adapted from (12) and describe irRC criteria and compare/contrast irRC criteria with standard WHO criteria.

Table 2. Derivation of irRC overall responses			
Measurable response	Nonmeasurable response		Overall response
Index and new, measurable lesions (tumor burden),* %	Non-index lesions	New, nonmeasurable lesions	Using irRC
↓100	Absent	Absent	irCR [†]
↓100	Stable	Any	irPR [†]
↓100	Unequivocal progression	Any	irPR [†]
↓≥50	Absent/Stable	Any	irPR [†]
↓≥50	Unequivocal progression	Any	irPR [†]
↓<50 to <25†	Absent/Stable	Any	irSD
↓<50 to <25†	Unequivocal progression	Any	irSD
≥25?	Any	Any	irPD [†]

*Decreases assessed relative to baseline, including measurable lesions only (>5 x 5 mm).
†Assuming response (irCR) and progression (irPD) are confirmed by a second, consecutive assessment at least 4 wk apart.

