2.2. Secondary Objectives

- To determine antitumor activity of ipilimumab therapy with BMS-986156 (30 or 100mg) as well as Nivolumab with BMS-986156 (30 mg) with SBRT treatment for 1-4 lung lesions in both the SBRT treated lesion and non-irradiate tumors.

- b) To determine antitumor activity of ipilimumab therapy with or without BMS-986156 (30 or 100mg) as well as Nivolumab with BMS-986156 (30 mg) with SBRT treatment for 1-4 liver lesions in both the SBRT treated lesion and non-irradiate tumors.
- c) To compare response and progression of the non-irradiated tumors between BMS-986156 with ipilimumab vs BMS-986156 with Nivolumab, using irRC.
- d) To evaluate the predictive potential value of tumor-associated and systemic immune biomarkers for therapy effectiveness and toxicity prediction.
- e) To evaluate whether skeletal mass, neutrophil, neutrophil to lymphocyte ratio, and tumor bulk are correlated with clinical outcomes and adverse events.
- f) To evaluate whether tumor kinetics in combination with clinical correlates can help determine treatment response. The radiological response and clinical data will be analyzed using mathematical and statistical models to identify prognostic groups.
- g) To evaluate whether tumor mutational burden correlates with improved clinical outcomes and response criteria.

3. Background

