Efficacy data from Phase I and II studies in melanoma suggest a trend of increasing durability and progression free survival (PFS) rates with increasing doses and duration of exposure to ipilimumab. However, preliminary data suggests that 10mg/kg of ipilimumab is associated with a higher frequency of SAEs and serious (Grade 3 or higher) irAEs than 3mg/kg of ipilimumab(2, 11, 12). It appears that an increased awareness and better management of these side effects has led to a decrease in their severity and an improvement in their control in recent trials. We propose to use ipilimumab at 3 mg/kg dose administered as 4 doses every 3 weeks and will implement a tight safety rule (see section 7.3) to stop the trial in case of excess toxicity.

It is important to note that because ipilimumab works indirectly through stimulation of the immune system by enhancing T-cell activation, its effect on tumor burden may take weeks to months to become apparent. The clinical activity of ipilimumab may manifest, not only as an early objective response, but also as stable disease (SD) with slow, continuous decline of tumor burden toward response and, in some cases, as a late objective response after initial tumor volume increase (12). For example, in one study (MDX010-19) the time to first response ranged from day 40 to day 441 (10). Durable responses and SD after treatment with ipilimumab have been observed in several malignancies, including melanoma, prostate and renal cell carcinoma.

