5.3.10 Dose Calculations

A total dose of 480 mg will be infused in a diluted form by mixing four 100 mg vials (10mL) plus 8 mL of a fifth vial into a sterile and compatible container, followed by the addition of 102 mL of 0.9% Sodium Chloride Injection, USP or 5% Dextrose Injection, USP. The total infusion volume will be 150 mL, which is within the acceptable range stated in the Nivolumab investigational brochure version 17. The infusion will take place over a 30 minute span resulting in an infusion rate of 5 mL/min.

6. Radiation Information

For the radiation in this trial we allow multiple tumor sites to be treated at the same time, for example physician can treat 3-4 lung lesions at the same time on this trial. Additionally palliative radiation needed for patient symptoms is allowed as standard of care and is allowed prior to the trial and during the trial as per the treating physician discretion.

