6.1. Dosimetry

All patients will receive stereotactic body radiation therapy (SBRT) for a total dose of 50 Gy with 12.5 Gy/fraction in 4 fractions or 60 Gy in 10 fractions prescribed to the planning target volume (PTV). It is recommended that prescribed isodose line cover more than 95% of the PTV if normal tissue dose is within threshold (as defined in 6.5). In the event that normal tissue dose is considered unacceptably high when treated with 50 Gy in 4 fractions, then patients can be alternatively treated with 60 Gy in 10 fractions. For lesion close to critical structures, compromised PTV coverage is allowed in order to meet normal tissue dose constraints. In this case, treating physician should make clinical judgments regarding optimal target coverage and normal tissues sparing.

There is no or little aperture margin recommended. The external border of the PTV will be covered by a lower isodose surface than usually used in conventional radiotherapy planning, which typically ranges from 70-95%. However, higher isodoses (hotspots) must be manipulated to occur within the target and not in adjacent normal tissue. Heterogeneity correction should be applied for planning. The recommended radiation dose and fraction will be either at the initial XRT dose (50 Gy in 4 fractions or 60 Gy in 10 fractions) lower dose may be used if felt to be clinically indicated by the treating physician. Other tumor sites may be treated for palliation concurrently or sequentially if needed at the discretion of the treating radiation oncologist.

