 - If 1 of 3 subjects have a DLT in dose level, 3 more patients will then be enrolled at this dose level. If only 1 of the 6 total subjects at dose level has a DLT, then this dose level will be considered safe and all other patient in this arm will be treated at this dose level.
 - If 2 of 6 subject has DLT then the dose will be de-escalated as per table below.
 - If 2 of 3 subjects have a DLT at dose level 1, then the dose will be de-escalated as per table below

Dose De-Escalation of BMS-986156 when combining with Nivolumab plus SBRT.

Dose Level 1	480mg Nivolumab + 30 mg BMS-986156
---------------------	------------------------------------

Dose Level -1 480mg Nivolumab + 10 mg BMS-986156**7.1.2. Reinduction for all arms**

Reinduction will be allowed for patients in which the treating physician feels there was benefit from the trial treatment. It will consist of repeating the original treatment using the same schedule for each arm. Radiation may be given during reinduction, but is not required. Pending the treating radiation oncologist judgment, additional radiation therapy to a previously non-irradiated lesion can be administered during re-induction. Timing of radiation during reinduction will be at the discretion of treating Radiation Oncologist.

The target lesion for radiation will be chosen by the treating radiation oncologist. The target lesion must not have been previously irradiated. The target lesion does not have to be within the same organ that was initially treated during the initial treatment (e.g. patients who received initial lung lesion irradiation can have liver or a bone lesion irradiated during re-induction). Radiation dose and fraction will be either at the initial dose (50 Gy in 4 fractions or 60 Gy in 10 fractions) or at a lower palliation dose (30 Gy in 10 fractions) and may also be combined with low dose radiation ranging from 200cGy-1000cGy in multiple fractions, at the discretion of the treating radiation oncologist.

Other tumor sites may be treated for palliation concurrently or sequentially if needed at the discretion of the treating radiation oncologist.

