7.8. Concomitant, Prohibited and Restricted Therapies During the Study

7.8.1. Concomitant Therapies

- All patients should have antiemetic medications available once discharged from the clinic. Oral antiemetic medications should be prescribed and administered as needed, and adjusted during the cycle at the discretion of the treating investigator.
- If patients experience nausea and vomiting despite the premedication, the patient may take PRN antiemetics per treating physician's discretion.
- All patients may have emollient or lubricating creams to be placed on the corresponding SBRT field for symptomatic skin irritation after SBRT treatment completion at the discretion of the treating investigator.

Radiation outside of the SBRT treatment fields will also be allowed based on the treating physician discretion.

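### Out-field response is defined by absence of protocol SBRT, not absence of radiation, so direct shrinkage of a palliatively or low-dose irradiated lesion can be scored as out-field response

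*Combined protocol and SAP*

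**What the plan says.** Section 2.2, objective c): "To compare response and progression of the non-irradiated tumors between BMS-986156 with ipilimumab vs BMS-986156 with Nivolumab".

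Section 8.5.1 builds the Out-Field burden from "SPD(all index lesions NOT targeted by SBRT in this protocol", plus measurable new lesions beyond the PTV. Sections 8.3 and 10.2.4 sort lesions the same way, by whether protocol SBRT treated them.

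Other radiation is permitted:
- Section 6 (opening): "palliative radiation needed for patient symptoms is allowed as standard of care and is allowed prior to the trial and during the trial".
- Section 6.1: "Other tumor sites may be treated for palliation concurrently or sequentially if needed".
- Section 7.8.1: "Radiation outside of the SBRT treatment fields will also be allowed based on the treating physician discretion". Section 7.8.2 narrows this while ipilimumab is being given, but exempts pain-controlling radiation where progression is not clear.
- Section 7.1.2 (re-induction, all arms): radiation may be at the initial SBRT dose "or at a lower palliation dose (30 Gy in 10 fractions) and may also be combined with low dose radiation" of 200 to 1000 cGy. On the choice of target: "The target lesion must not have been previously irradiated".

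Sections 8.3 and 10.2.4 both count imaging taken during and after re-induction toward best response. Section 10.2.1 describes the group comparisons as exploratory.

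**The concern.** The objective is about tumour that received no radiation, but the measure selects tumour that received no protocol SBRT. No section removes a palliatively or low-dose irradiated lesion from the out-field sum, relabels it, or stops counting scans after that radiation.

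Re-induction makes this more than a theoretical gap. Its target must be a lesion not irradiated before, so in groups 2 and 3 it cannot come from the initial SBRT course. If it is an index or measurable new lesion, it was out-field until then. Group 1 has no initial SBRT, so all its lesions are out-field, yet re-induction radiation is open to it too.

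Where re-induction uses an SBRT dose, the text does not say whether, or from when, the lesion becomes in-field.

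Response outside the field is the trial's rationale (section 3.3). If part of it is direct radiation effect, the out-field rate no longer answers objective c).

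**Working it through.** **1. The plan's own figure.** Section 10.2.4 states 80% power with 20 per arm, two-sided alpha 10%, chi-squared test. The uncorrected test gives 80.0%, 79.4%, 79.4% and 80.7% for 44 vs 10, 57 vs 20, 68 vs 30 and 78 vs 40%. The figure is sound and is not in dispute here.

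**2. Effect on irPR.** irPR needs a fall of at least 50% from baseline (section 8.5.1). Assume k equal out-field lesions, one irradiated and shrinking by fraction s. The shrinkage needed in each of the others is

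(0.5 − s/k) / (1 − 1/k).

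| s | k = 2 | k = 3 | k = 15 |
|---|---|---|---|
| 1.0 | 0% | 25% | 46% |
| 0.8 | 20% | 35% | 48% |
| 0.6 | 40% | 45% | 49% |
| 0.5 | 50% | 50% | 50% |
| 0.3 | 70% | 60% | 51% |

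Without radiation to any lesion the requirement is 50%. Both k and s are assumptions; the documents give no shrinkage data for these doses.

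**3. After earlier progression.** Section 1 offers re-induction to patients who benefit but later progress. Take two lesions of 10 units, each grown 25% to 12.5. Baseline is 20, so the sum must reach 10.
- s = 1.0: the other must fall to 10, its baseline size.
- s = 0.8: the irradiated lesion is 2.5, so the other must reach 7.5 (25% below baseline).
- s = 0.6: the irradiated lesion is 5, so the other must reach 5 (50% below baseline). The advantage is gone.

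**4. Masking of irPD.** irPD needs a 25% rise from nadir. With two lesions of 10 and nadir equal to baseline, the sum must reach 25. If the irradiated lesion shrinks 100%, 80% or 60%, the other can grow to 25, 23 or 21 (150%, 130% or 110%). If the first lesion merely stayed stable, the limit is 15 (50%).

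**5. Patient level.** 1/20 = 5 points. Section 10.2.4 estimates success separately for liver and lung, so the denominators there are smaller. With an assumed 10 patients at a site, 1/10 = 10 points. Section 3.3 cites a previous out-of-field irPR rate of 10%.

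**6. Time available for confirmation.** Cycle 4 falls on day 64 in groups 1 and 2 and on day 85 in group 3. The section 12 calendars allow re-induction from 8 weeks later: 64 + 56 = day 120 and 85 + 56 = day 141. Taking the weeks named in section 8.3 as the first countable scan gives days 85–91 and days 64–70. The gap to earliest re-induction is:
- groups 1 and 2: 120 − 91 = 29 to 120 − 85 = 35 days;
- group 3: 141 − 70 = 71 to 141 − 64 = 77 days.

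Routine rescans come at 12 ± 4 weeks, or 56 to 112 days. None fits before the earliest re-induction in groups 1 and 2, while one can fit in group 3. These days are approximate: section 8.3 counts imaging after those weeks, and section 7.3.3 gives an 8-weekly schedule instead.

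**The case against.** **Re-induction may follow progression.** On the section 1 route, the step 2 figures are too favourable to the concern, and step 3 applies. This stands. The section 12 calendars instead offer re-induction after SD or PR, and the two are not reconciled.

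**An earlier best response is already secured.** A reader might infer from step 4 that masked progression inflates treatment success. The documents do not support that in general. Best response is taken over all imaging, so an irSD or irPR before re-induction already counts, and overall survival is the only time-to-event analysis in section 10.2.4. Masking matters mainly for irSD beyond 6 months, or when palliation precedes any benefit.

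**The irradiated site may be outside the sum.** Section 7.1.2 mentions a bone lesion and section 7.8.2 describes palliation as pain-controlling, so some irradiated sites may be neither index nor measurable new lesions. This stands, and it is one reason why no frequency can be given.

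**Re-induction radiation may be SBRT.** Section 1 describes it as similar to the initial course, and such a lesion could be read as targeted by protocol SBRT. That is arguable. It does not cover the lower-dose options in section 7.1.2 or palliation.

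**The biopsy wording.** A reader might take section 8.2.5 as a deliberate rule separating low-dose-irradiated from non-irradiated tumour. The sentence is too unclear to carry that weight.

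**Conclusion.** The mismatch is real and rests on the text: the out-field rule can score direct radiation shrinkage as response of tumour that objective c) treats as non-irradiated. It should be corrected, but it does not threaten the trial's main result. The comparisons are secondary and exploratory, and the primary safety result is unaffected.

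The size is unknown. The effect on irPR is large only with few out-field lesions and marked shrinkage of the irradiated one. Without prior growth it is nil at 50% shrinkage, and below that irPR becomes harder.

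A reader might go further and infer that the out-field rate is inflated by a known amount, or that one regimen is favoured. The documents support neither, since they give no frequency of such radiation by group and no shrinkage data.

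**What to change.** 1. Record the site and date of every on-study radiation course against each index and measurable new lesion.
2. For objectives a) to c), report out-field best response from scans before the first on-study radiation to any out-field index or measurable new lesion, with labels set by the initial SBRT course. Place it beside the planned all-imaging result, with affected patients flagged. A response first documented before that date stands if a later scan confirms it in the lesions still not irradiated, using the same lesion set at baseline and follow-up. Show by group how many were confirmed this way, and the rate with and without them. Simply calling them unconfirmed would fall harder on groups 1 and 2 (working, step 6).
3. Keep patients irradiated before their first countable scan in the denominator, show their number by group, and give the rate without them as a check.
4. In the all-imaging result, count a lesion given SBRT at re-induction as in-field from that date, with one lesion set in the baseline, nadir and follow-up sums. Otherwise, with two stable lesions of 10, dropping one at follow-up only turns 20 into 10, a false 50% fall.
5. Reconcile who may receive re-induction (section 1 against the section 12 calendars) and the scan timing (section 7.3.3 against section 8.3).

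Separate minor point: section 8.5.1 ties clinical benefit to irSD lasting up to 6 months, while section 10.2.4 requires more than 6 months. Reconcile them.

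**Cost.** Lesion-level linkage of radiation, which the documents do not show is now captured. Out-field follow-up is shorter in irradiated patients, so some late responses are lost: section 3.1.1 reports of one ipilimumab study that "the time to first response ranged from day 40 to day 441". Out-field rates will be somewhat lower. With an assumed 3 responders, keeping early-irradiated patients gives 3/20 = 15.0%, against 3/18 = 16.7% if two were excluded. No treatment rule changes.

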8.6 Systemic Biomarkers

The objective of this portion of the study is to correlate systemic serum markers, obtainable by peripheral venous access to patient responses and observed toxicities. Participation in this portion of the protocol is mandatory for all study participants.

Systemic lymphocyte counts obtained from routine CBC with differential will be analyzed and associated with clinical outcomes and toxicities from the lab draws obtained throughout this protocol.

